15.5 Child Behavior Checklist

The Child Behavior Checklist (CBCL) questionnaire is captured at Screening, Week 26 and Week 52. All summaries will be generated on the Safety Population and include all assessments recorded up to 30 days following treatment discontinuation. Listings will include all reported data.

The CBCL 1.5-5 years old and the CBCL 6-18 years old comprise questions addressing symptoms related to mood, behavior issues, and sleep disturbance. It is completed by the parent or primary caregiver.

The CBCL 1.5-5 years old is used in this study for children aged 5 to < 6 years old. It consists of 100 questions, scored on a three-point Likert scale (0=Not True (as far as you know), 1= Somewhat or Sometimes True, 2=Very True or Often True). The time frame for item responses is the past 2 months.

The CBCL 6-18 years old is used in children aged 6 up to 18 years old. It consists of 113 questions, scored on a three-point Likert scale (0=Not True (as far as you know), 1= Somewhat or Sometimes True, 2=Very True or Often True). The time frame for item responses is the past six months.

	Study 111-301 Statistical Analysis Plan
---	--

Note: No data is collected from the language scale, as it is supplemental and not required to calculate any of the behavior measures.

The checklist yields scores in the following areas:

CBCL 1.5-5	CBCL 6-18

 • Emotionally reactive • Anxious/Depressed • Withdrawn • Somatic Complaints • Attention Problems • Aggressive Behavior 	
 • Anxious/Depressed • Withdrawn/Depressed • Somatic Complaints • Social problems • Thought Problems • Attention Problems • Rule Breaking Behavior

The table in Appendix 23.1 shows how the domains are constructed with regards to the individual questions. The scores for each individual question within a domain are summed to give a domain score.

Each domain score above and total score will be summarized (n, mean, SD, median, 25th and 75th percentile, minimum, maximum) by treatment group at Baseline, Week 26 and Week 52, as will change from baseline at Week 26 and Week 52 (where baseline measures exist).

Where possible, the CBCL 1.5-5 and CBCL 6-18 will be summarized together. If a subject progresses during the course of the study from one version to the next the results will be summarized together and the baseline assessment from the child's first questionnaire (1.5-5) will be referred to when summarizing change from baseline.

Domain scores and total score will be listed by treatment group and subject number.

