9.12.6.7 Child Behavior Checklist

The CBCL 1.5 - 5 and the CBCL 6 - 18 comprise questions addressing symptoms related to mood, behavior issues, and sleep disturbance. It is completed by the parent or primary caregiver. The CBCL 1.5 - 5 years old should be used in children aged 5 to < 6 years old. The CBCL 6 - 18 years old should be used in children aged 6 up to 18 years old. No data will be collected from the language scale, as it is supplemental and not required to calculate any of the behavior measures.

The form requires approximately 15 minutes to complete. The checklist yields scores in the following areas: reactivity, anxiety, depression, somatic complaints, withdrawal, sleep problems, attention problems, and aggressive behavior.

The CBCL assessment will be implemented in those countries where country-specific versions are available.

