**Study 111-301 Statistical Analysis Plan****5 GENERAL ANALYSIS CONSIDERATIONS**

The analyses described in this SAP are based on Amendment 4 of the protocol (dated 01-February-2019).

Individual subject data that is reflected in data summaries will be provided in **PI**. Unless otherwise specified, all **PI** will be by treatment group and ordered by subject number, where subject number includes the site number.

Summary tables and figures are provided by treatment group with no overall population column. There are certain exceptions (e.g. subject disposition, demographics, baseline characteristics and safety data) which are indicated in the relevant sections.

Baseline annualized growth velocity (AGV) is defined in Section 14.3.1. Baseline growth measures (other than AGV) and baseline weight are those assessed on Day 1 of dosing, regardless of timing relative to dosing. (Note: If no assessments are available, then the baseline assessment will be the last non-missing assessment prior to Day 1). All other baseline assessments are the last non-missing on-study 301 assessments prior to administration of study drug. Change from baseline is calculated as: [post-baseline value – baseline value]; Percent change from baseline is calculated as: ([post-baseline value – baseline value]/baseline value) x 100.

The Screening visit will not be presented in descriptive summaries over time. When the analysis windows have been applied (see Section 5.4), data collected at the screening visit may be included in the Baseline assessment. All assessments will be listed, but only those assessments assigned to visits according to the windows applied (see Section 5.4) will be summarized in tables or graphically. Exceptions to this are summaries of the worst post-baseline laboratory data in shift tables where all assessments are considered, and also the standing height assessments displayed in the spaghetti plots.

Unless otherwise specified, the number of subjects, mean, 25th percentile, median, 75th percentile and estimates of precision (e.g. SD, confidence interval) will be displayed to one more decimal place than the collected data. Minimum and maximum values will be presented to the same decimal places as the collected data. For summaries by visit, the number of subjects with non-missing observations (n) according to the analysis windows (see Section 5.4 for further details) at the derived visit will be presented.

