14.5.5.1 Pediatric Quality of Life Inventory (PedsQL)

The PedsQL scales were designed to measure the core dimensions of health, as delineated by the WHO, as well as role (school) functioning. The following versions of the PedsQL are utilized in this protocol:

Parent/Caregiver Reported

- Parent Proxy-Report Children Ages 5-7
- Parent Proxy-Report Children Ages 8-12
- Parent Proxy-Report Adolescents Age 13-18

Self-Reported

- Child Self-Report Ages 8-12

Study 111-301 Statistical Analysis Plan

- Adolescent Self-Report Ages 13-18

The PedsQL consists of 4 scales of functioning (Physical, Emotional, Social, and School), which make up 3 summary scores.

Each of the items within a scale is scored as 0 (never a problem), 1 (almost never a problem), 2 (sometimes a problem), 3 (often a problem), to 4 (almost always a problem). Items are then reverse scored and linearly transformed to a 0-100 scale as follows: 0=100, 1=75, 2=50, 3=25, and 4=0.

Scales/Domains:

- Physical Functioning (8 items, min score=0, max score=800)
- Emotional Functioning (5 items, min score=0, max score=500)
- Social Functioning (5 items, min score=0, max score=500)
- School Functioning (5 items, min score=0, max score=500)

If at least 50% of items are completed within a scale, then the **mean score** is calculated for each scale using the transformed values:

$$\text{Scale/Domain Score} = \frac{\text{Sum of item scores}}{\text{Number of items answered}}$$

If more than 50% of the items are missing within a scale, then scale scores should not be calculated and be set to missing. (Varni, 1999)

For each of the scales, the mean scores (based on transformed values), and change from baseline at each scheduled visit, will be summarized (n, mean, SD, median, 25th and 75th percentile, minimum, maximum) by treatment group.

Summary scores:

In addition to the mean scale scores, the following summary scores will be calculated. All calculations use the transformed data.

- Psychosocial Health Summary Score (Sum of item scores/Number of items answered on Emotional, Social and School scales)
- Physical Health Summary Score (Sum of item scores/Number of items answered on Physical scale)
- Total Score (Mean Score, i.e., Sum of all items/Number of items answered on all scales)

For each of the above summary scores, the absolute values, and change from baseline at each scheduled visit, will be summarized (n, mean, SD, median, 25th and 75th percentile,

Study 111-301 Statistical Analysis Plan

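### For children who move from the CBCL 1.5-5 to the CBCL 6-18, change from baseline subtracts raw item sums of two different questionnaires and cannot be read as a change in behavior

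*SAP*

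**What the plan says.** SAP 15.5 uses the CBCL 1.5-5 for children aged 5 to under 6 and the CBCL 6-18 from age 6, at Screening, Week 26 and Week 52. Four rules combine:

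- Domain scoring: "The scores for each individual question within a domain are summed to give a domain score".
- Version-changers: "If a subject progresses during the course of the study from one version to the next the results will be summarized together", and the child's "first questionnaire (1.5-5) will be referred to when summarizing change from baseline".
- Change, from SAP 5: "Change from baseline is calculated as: [post-baseline value – baseline value", a simple difference.
- Reporting: "Each domain score above and total score will be summarized" by arm, including minimum and maximum.

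Neither SAP 15.5, SAP Appendix 23.1 nor Protocol 9.12.6.7 gives a norm-based score, item mean or other common scale for the CBCL. The items behind the total score are not stated for either version. SAP 15.5 pools the two versions only where that can be done, but the sentence on children who change version carries no such limit.

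**The concern.** Followed literally, the rule subtracts a score on one instrument from a score on another. The two forms differ in item content and recall period (2 months against 6) and, in some domains of the same name, in length. A child whose behavior is unchanged can show a non-zero change because the form changed.

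The SAP avoids this elsewhere. PedsQL age versions are also pooled, but on a length-free scale: "Items are then reverse scored and linearly transformed to a 0-100 scale as follows", and then averaged over the items answered (SAP 14.5.5.1). For DXA, subjects measured on more than one scanner type are left out of the summaries and only listed (SAP 16.4).

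At stake is how the CBCL safety table reads. The maximum or minimum change in an arm may come from a switch of questionnaire, and nothing in the SAP says the table will mark it.

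**Working it through.** The plan states no sample size, power or expected value for the CBCL, so there is no figure to reproduce.

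**Scale lengths.** Items counted in SAP Appendix 23.1. Each item scores 0 to 2, so maximum = 2 × items.

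| Domain | 1.5-5: items (max) | 6-18: items (max) |
|---|---|---|
| Anxious/Depressed | 8 (16) | 13 (26) |
| Attention Problems | 5 (10) | 10 (20) |
| Somatic Complaints | 11 (22) | 11 (22), partly different items |
| Aggressive Behavior | 19 (38) | 18 (36) |

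The list in SAP 15.5 shows Aggressive Behavior only under the 1.5-5 form; the appendix has it under both. If the total score sums the mapped items, it is 60 against 104 items (maximum 120 against 208). If it sums all questions, it is 100 against 113.

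**Who switches.** There is no Day 0 (SAP 5.3), so Day −m to Day n spans n + m − 1 days. Screening is Day −30 to Day −1. With birthdays uniform over the year (assumption), the share of children screened at age 5 who have turned 6 is days/365.25, capped at 100%.

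| Visit and window | Days from Screening | Share switched |
|---|---|---|
| Week 52, SAP 5.4 (Day 344 to 386) | 344 to 415 | 94% to 100% |
| Week 26, SAP 5.4 (Day 162 to 204) | 162 to 233 | 44% to 64% |
| Week 52, protocol ±7 days | 358 or more | 98% to 100% |
| Week 26, protocol ±7 days | 176 to 219 | 48% to 60% |

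**Size for one child.** If the mean item score m is the same on both forms (assumption), the change with no real change is (items in 6-18 − items in 1.5-5) × m. Both Anxious/Depressed and Attention Problems gain 5 items, so m = 0.1 gives 5 × 0.1 = +0.5 and m = 0.5 gives 5 × 0.5 = +2.5. The sign reverses if the 6-18 mean item score is below 8/13 = 62% (Anxious/Depressed) or 5/10 = 50% (Attention Problems) of the 1.5-5 one. The documents do not say which applies.

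**Size for the summaries.** The number of 5-year-olds is not given. With ages uniform over 5 to under 18 (assumption), 110/13 = 8.5, so about 8 switchers, 4 per arm. With shifts of 0.5 and 2.5 and an assumed SD of 2:

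- Mean: 0.5 × 8/110 = 0.04; 2.5 × 8/110 = 0.18.
- 75th percentile (normal mixture, 8/110 shifted): +0.04 and +0.22.
- SD: √(4 + (8/110)(102/110) × 2.5²) = 2.10 at most.

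**Size for the maximum.** Simulated chance that the largest increase in an arm of 55 belongs to one of 4 switchers (normal changes, at least 100,000 runs):

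| Shift | SD 2 | SD 4 |
|---|---|---|
| 0 | 7% | 7% |
| +0.5 | 12% | 9% |
| +2.5 | 51% | 23% |

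**The case against.** The strongest reply is that little depends on this. The CBCL is a descriptive safety measure with no test. Its main use is the comparison of arms, and randomization balances the artefact in expectation. The SAP prespecifies its rule openly and uses the same baseline rule for the age versions of its quality-of-life questionnaires (SAP 14.5.5). Extremes can be traced, since "Domain scores and total score will be listed by treatment group and subject number". All of that stands, and it is why the point is minor. It does not make the difference for a version-changer meaningful, and the SAP does not say that the listing will show which form was used.

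The limits on pooling, and the restriction of change to cases with a baseline, drop domains that have no counterpart (Emotionally Reactive, Social Problems, Thought Problems, Rule Breaking). They do not help the domains that appear on both forms.

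The size figures rest on assumptions. The cap of 20% above Tanner Stage 1 makes an even age spread to 18 doubtful. If 80% of 110 were spread over 5 to under 11 (illustration), 88/6 gives about 15 switchers and the mean would move 0.07 to 0.34, which is larger but still small. There may be fewer switchers too: "The CBCL assessment will be implemented in those countries where country-specific versions are available". The 51% is the top of its range. It needs a mean item score of 0.5, SD 2 and continuous changes. With the same changes rounded to whole points, a switcher is the sole maximum in about 39% of runs, against about 4% with no shift.

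**Conclusion.** The concern holds, as a minor correction. For nearly every child screened at age 5, the Week 52 CBCL change will be a difference between two questionnaires, and so will about half of the Week 26 changes. The mismatch is plainest for Anxious/Depressed, Attention Problems and the undefined total score. Somatic Complaints and Aggressive Behavior have equal or nearly equal lengths, but their items and recall periods still differ.

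The direction of the distortion is not determined by the documents. The effect on arm means, quartiles and SDs is small under every switcher count tried, and the between-arm contrast is unbiased in expectation. The practical harm is to individual changes and to the reported extremes. How large that is depends on the assumed item scores, SD and number of switchers, none of which the documents give.

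**What to change.** Amend SAP 15.5 as follows:

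1. Compute CBCL change from baseline only when the same version was used at both visits, and summarize the two versions separately.
2. Show version-changers in a separate row or listing that gives the form used at each visit.
3. State which items make up the total score for each version, and do not difference it across versions.

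A weaker alternative is a mean item score per domain with a footnote that items and recall periods still differ. It removes the effect of scale length but not the difference in content.

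The cost is SAP wording and table shells; no data collection changes. The drawback is that nearly all children screened at age 5, the youngest enrolled, leave the Week 52 change summary and about half leave the Week 26 one. Unlike the DXA scanner exclusion, this loss is systematic by age, so the separate row is needed to keep them visible.

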15.6 Echocardiogram

Echocardiogram results are only collected at the Screening visit, and will be listed by treatment group and subject.

15.7 On-Study Procedures, Interventions and Surgeries

Any procedures, interventions or surgeries that occur on study (post first dose of study drug) will be captured, along with start and stop date. These will be coded using the latest available MedDRA version and details provided in a listing.

15.8 Hip Monitoring and Rotation

All hip monitoring clinical assessments, including hip rotation, will be listed by treatment group, subject and assessment date.

**Study 111-301 Statistical Analysis Plan****15.9 Pregnancy Testing**

A pregnancy test will be performed at the following visits for female subjects who have begun menses or are ≥ 10 years of age; Screening, Day 1, Week 6, Week 13, Week 26, Week 39, Week 52, Early Termination and at the Safety Follow-up visit.

PI

**Study 111-301 Statistical Analysis Plan****16 IMAGING SECONDARY ENDPOINT(S)**

All summaries of imaging data will be based on the Safety Population. All visits referred to in the analyses, are based on the analysis windows described in Section 5.4. Therefore, where summaries are based on data collected at the Screening visit, they will be referred to as Baseline assessments once the analysis window is applied.

16.1 Bone Age

An X-ray of the left hand and wrist will be performed at Screening, Week 26 and Week 52, and bone age determined using the Greulich and Pyle Atlas.

Bone age at Baseline, Week 26 and Week 52, and change from baseline at Week 26 and Week 52 will be summarized (n, mean, SD, median, 25th and 75th percentile, minimum, maximum) by treatment group and presented by sex and overall.

Each measurement of bone age will be converted to an age-and sex-appropriate standard deviation score (SDS), also referred to as a Z-score, by comparison with reference data available for average stature children (Greulich and Pyle, 1959). Bone age Z-scores at Baseline, Week 26 and Week 52, and change from baseline at Week 26 and Week 52 will be summarized (n, mean, SD, median, 25th and 75th percentile, minimum, maximum) and presented by treatment group.

In addition, for the visits at Baseline and Week 52, scatter plots will be provided which display bone age z-score on the y-axis, and age in years at that visit on the x-axis, identifying the two treatment groups. A separate plot will be generated for each sex and overall.

16.2 Lower Limb X-Rays

For each of the following parameters, excluding femur length, the absolute values for both the left and right leg at Baseline, Week 26 and Week 52, and change from baseline at Week 26 and Week 52 will be summarized (n, mean, SD, median, 25th and 75th percentile, minimum, maximum) and presented by treatment group for each baseline age category (≥ 5 to < 8 , ≥ 8 to < 11 , ≥ 11 to < 15 , ≥ 15 to < 18 years). As the assessment of femur length was introduced mid-study, subjects will not have a measurement of femur length at baseline, and data will be listed only.

- Left/Right Femur length (cm)
- Left/Right Tibia length (cm)
- Left/Right Fibula length (cm)

Study 111-301 Statistical Analysis Plan

- Left/Right Tibia bowing angle (degrees)
- Left/Right Distance between ankle joint and distal growth plate of fibula (cm)

In addition, change from baseline in tibial length (y-axis) at Week 52 will be presented on a boxplot, with a separate box for each leg and treatment group with baseline age category (≥ 5 to < 8 , ≥ 8 to < 11 , ≥ 11 to < 15 , ≥ 15 to < 18 years) on the x-axis. A similar plot will also be generated for change from baseline in fibula length at Week 52.

All assessments will be listed by treatment group, subject and visit.

16.3 Lumbar Spine X-Rays

Lumbar spine x-rays (AP and lateral views) are performed at Screening and Week 52. Assessments will be listed by treatment group, subject and visit.

16.3.1 Vertebral Height

Vertebral heights (anterior, medial, and posterior) will be measured for each individual vertebra (L1, L2, L3, L4, and L5).

The following ratios will be calculated for each individual vertebra (L1, L2, L3, L4, and L5) and reported to 1 decimal place:

- Anterior height (cm) to medial height (cm)
- Anterior height (cm) to posterior height (cm)
- Medial height (cm) to posterior height (cm)

For each of the above ratios, the absolute values at Baseline and Week 52, and change from baseline at Week 52 will be summarized (n, mean, SD, median, 25th and 75th percentile, minimum, maximum) and presented by treatment group.

16.3.2 Transverse Diameter (Interpedicle Distance)

The transverse diameter (interpedicle distance) will be measured for each individual vertebra (L1, L2, L3, L4, and L5) at Baseline and Week 52.

For each vertebra, the absolute values at Baseline and Week 52, and the change from baseline at Week 52 will be summarized (n, mean, SD, median, 25th and 75th percentile, minimum, maximum) and presented by treatment group for each baseline age category (≥ 5 to < 8 , ≥ 8 to < 11 , ≥ 11 to < 15 , ≥ 15 to < 18 years).

In addition, change from baseline in transverse diameter (y-axis) for each individual vertebra (x-axis) will be presented on a boxplot at Week 52 for each treatment group. Separate plots

Study 111-301 Statistical Analysis Plan

will be generated for each baseline age category (≥ 5 to < 8 , ≥ 8 to < 11 , ≥ 11 to < 15 , ≥ 15 to < 18 years).

16.3.3 Sagittal Width

The spinal canal width (sagittal width) will be measured for each individual vertebra (L1, L2, L3, L4, and L5) at Baseline and at Week 52.

For each individual vertebra, the absolute values at Baseline and Week 52, and the change from baseline at Week 52 will be summarized (n, mean, SD, median, 25th and 75th percentile, minimum, maximum) and presented by treatment group for each baseline age category (≥ 5 to < 8 , ≥ 8 to < 11 , ≥ 11 to < 15 , ≥ 15 to < 18 years).

In addition, change from baseline in sagittal width (y-axis) for each individual vertebra (x-axis) will be presented on a boxplot at Week 52 for each treatment group. Separate plots will be generated for each baseline age category (≥ 5 to < 8 , ≥ 8 to < 11 , ≥ 11 to < 15 , ≥ 15 to < 18 years).

16.3.4 Lumbar Spine Angles

The following angles will be measured on the lumbar spine x-rays:

- Sacral tilt (degrees)
- Lordosis (inward curve of the spine) (degrees)
- Kyphosis (convex curvature of the spine) (degrees)

Each angle will be measured on the spine x-rays and compared to Baseline at Week 52 to determine any worsening of sacral tilt, lordosis (inward curve of the spine) or kyphosis (convex curvature of the spine).

The absolute values of the sacral tilt, lordosis and kyphosis angles at Baseline and Week 52, and change from baseline at Week 52 will be summarized (n, mean, SD, median, 25th and 75th percentile, minimum, maximum) and presented by treatment group for each baseline age category (≥ 5 to < 8 , ≥ 8 to < 11 , ≥ 11 to < 15 , ≥ 15 to < 18 years).

The following summaries will similarly be presented for each baseline age category (≥ 5 to < 8 , ≥ 8 to < 11 , ≥ 11 to < 15 , ≥ 15 to < 18 years):

A worsening in sacral tilt angle will be summarized [n(%)] by treatment group as follows:

- Percentage of subjects with an increase in sacral tilt angle of ≥ 5 to < 10 degrees at week 52
- Percentage of subjects with an increase in sacral tilt angle of ≥ 10 degrees at week 52

Study 111-301 Statistical Analysis Plan

A worsening in lumbar lordosis will be summarized [n(%)] by treatment group as follows:

- Percentage of subjects with an increase in lordosis angle of ≥ 5 to < 10 degrees at week 52
- Percentage of subjects with an increase in lordosis angle of ≥ 10 degrees at week 52

A worsening in kyphosis angle will be summarized [n(%)] by treatment group as follows:

- Percentage of subjects with an increase in kyphosis angle of ≥ 5 to < 10 degrees at week 52
- Percentage of subjects with an increase in kyphosis angle of ≥ 10 degrees at week 52

